12. DATA AND SPECIMEN BANKING*

N/A

13. Data Analysis and Management*

Sample size calculation

In order to obtain a sample size of 72 parent-child dyads to complete the research, we will potentially enroll up to 100 parent-child dyads. Because pilot studies do not provide meaningful estimates of effect sizes for between-condition comparisons, due to the imprecision inherent in data from small samples^{19,20} we base our proposed sample size of 72 parent-child dyads (36 per condition, 18 per practice) on pragmatics of recruitment, retention and the necessities for examining feasibility, providing important information for design and recruitment for the future R01 study to test the impact of Asthma Link™ in a large cluster RCT. We will identify refinements required to implement the large cluster RCT by obtaining data about several process outcomes as well as feasibility of recruitment, retention, engagement, fidelity and assessment procedures of Asthma Link™.

Taking estimation of retention rate as an illustrative outcome, and applying an intra-class (pediatric practice) correlation of 0.01, similar to the value of 0.006 from [name] prior studies of school-based teen smoking, the resulting design effect= $1.19 = 1 + [1 + 0.01 \times 9]$ ²¹ yields an effective sample size of $20/1.09 \approx 18$ dyads/condition. For a conservatively low retention rate of 80%, lower than the 97% observed in [name] previous FITLINE study,¹⁸ we can estimate a 95% confidence interval for retention percent of (51.9%, 95.7%) for each practice separately or (68.9%, 88.5%) combining all 4 practices. A sample of 18 dyads per practice (36 per condition) yields 95% confidence intervals for practice ICC of (0.018, 0.094) for a conservatively large true ICC=0.05.²² Because estimates from pilot studies alone tend to be underpowered due to the variability in estimated standard errors,^{19,20} we will combine our results (including the ICC) with clinically meaningful effect and results of previous adequately powered interventions to calculate sample size requirements for our large cluster RCT. Data from the recruited pediatric practices show that 5-7 very poorly controlled asthmatics are seen per month.

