22. SETTING

This pilot feasibility study will take place in 4 Pediatric Primary Care practices in Worcester MA: Benedict Pediatrics, Worcester Pediatrics, Quality Kids and Harding Pediatrics. These particular sites were selected due to their high rates of asthma and matching for relevant demographics. We have worked with these sites in [name] prior FITLINE study. If there are logistical issues with any of these practices after commencement of funding, we have identified 4 alternative practices in Worcester as backups.

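### The pooled retention interval carries no clustering allowance, and the practice ICC of 0.01 said to be applied is weakly supported; restate it with the design effect and over a range of ICCs

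*Combined protocol and SAP*

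**What the plan says.** Section 13 (Sample size calculation) bases the sample of "72 parent-child dyads (36 per condition, 18 per practice") on pragmatic grounds and then takes retention as an example of the precision available. Section 4 names retention as one of three primary trial outcomes.

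The calculation proceeds by "applying an intra-class (pediatric practice) correlation of 0.01, similar to the value of 0.006 from [name] prior studies of school-based teen smoking". A design effect is printed as 1.19, with an expression beside it that does not evaluate to 1.19, and the next step divides by 1.09: it "yields an effective sample size of $20/1.09 \approx 18$ dyads/condition".

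The retention rate is set cautiously: "For a conservatively low retention rate of 80%, lower than the 97% observed in" the FITLINE study. The 95% intervals given are ("51.9%, 95.7%) for each practice separately or (68.9%, 88.5%) combining all 4 practices").

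A larger ICC appears in the next sentence, for another purpose, namely the precision with which the ICC itself can be estimated: the sample "yields 95% confidence intervals for practice ICC of (0.018, 0.094) for a conservatively large true ICC=0.05".

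Section 22 says of the four practices: "We have worked with these sites in [name] prior FITLINE study".

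**The concern.** Two things are unsatisfactory.

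First, the only stated support for a practice-level ICC of 0.01 is a value from school-based work on teen smoking. Here the randomised cluster is the pediatric practice (section 11) and the quantity is the proportion of dyads retained. The documents give no reason why the earlier value should describe how dropout clusters by practice. The paragraph is cautious about the retention rate and about the ICC when it estimates the ICC, but shows retention precision at one low ICC only.

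Second, the reader is led to believe that the retention intervals allow for clustering. If the pooled interval does not, the plan claims more precision for a primary outcome than its own assumptions give. Retention is the only outcome rate for which section 13 shows precision, and the retention and ICC estimates are meant to inform the sample size of the later cluster trial.

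**Working it through.** **Inputs.** From section 13: 72 dyads, 18 per practice, retention 80%, ICC 0.01 (source value 0.006), larger ICC 0.05. From section 11: four practices. From section 25: 100 dyads enrolled, 25 per practice, to retain 72.

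**Method.** Design effect DE = 1 + (m − 1) × ICC, with m dyads per practice. Effective n = n / DE. The interval is the exact (Clopper-Pearson) 95% interval at 0.80 × effective n, using beta quantiles so that a non-integer effective n is allowed.

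**Step 1: the printed design effect.** The printed expression is 1 + [1 + 0.01 × 9] = 2.09, not 1.19. A value of 1.19 needs m = 20 (1 + 19 × 0.01), and 1.09 needs m = 10 (1 + 9 × 0.01). The stated 18 per practice gives 1 + 17 × 0.01 = 1.17. The numerator of 20 per condition matches the 40 children mentioned in section 24, not the 36 per condition of section 13.

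**Step 2: the printed pooled interval.** The exact interval at n = 72 with DE = 1 is 68.9% to 88.5%, width 19.6 points. This is the printed interval to the decimal. At effective n = 72 / 1.17 = 61.5 the exact interval is 67.9% to 89.1%. Wald, Wilson (with and without continuity correction), Jeffreys and Agresti-Coull limits at 61.5 do not give the printed pair either. The nearest, Jeffreys, gives 68.8% to 88.5% and does not fit the per-practice interval.

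**Step 3: the printed per-practice interval.** The exact interval for 12 of 15 is 51.9% to 95.7%, as printed. Fifteen is 18 / 1.17 = 15.4, or 18 / 1.19 = 15.1, cut to a whole number. Within one practice no between-practice allowance is needed, and n = 18 gives 54.8% to 94.8%. So a design effect seems to have been used where it is not needed and left out where it is.

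**Step 4: the pooled interval with the design effect applied (72 dyads, m = 18).**

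| ICC | DE | Effective n | 95% interval | Width (points) |
|---|---|---|---|---|
| none (as printed) | 1 | 72 | 68.9–88.5% | 19.6 |
| 0.006 | 1.102 | 65.3 | 68.3–88.9% | 20.6 |
| 0.01 | 1.17 | 61.5 | 67.9–89.1% | 21.3 |
| 0.02 | 1.34 | 53.7 | 66.8–89.7% | 22.8 |
| 0.03 | 1.51 | 47.7 | 65.9–90.2% | 24.3 |
| 0.05 | 1.85 | 38.9 | 64.1–91.1% | 27.0 |

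The lower limit falls by 1.0 point (68.9 to 67.9) from applying the plan's own ICC, and by a further 3.8 points (67.9 to 64.1) if the ICC is 0.05.

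**Step 5: the other denominator (100 enrolled, m = 25).** At ICC 0.01, DE = 1 + 24 × 0.01 = 1.24, effective n = 80.6, interval 69.6% to 88.1%, width 18.5 points. At ICC 0.05, DE = 2.20, effective n = 45.5, interval 65.5% to 90.4%, width 24.9 points.

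**Step 6: few clusters.** Steps 4 and 5 treat the design effect as known. A t interval on 3 degrees of freedom (four practices, t = 3.182, 72 dyads) is 0.80 ± 3.182 × √(0.16 / 61.5), or 63.8% to 96.2%, at ICC 0.01. At ICC 0.05 it is 59.6% to 100% (upper limit truncated). The exact intervals above are therefore on the optimistic side.

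**The case against.** The strongest case against is that little hangs on this. Retention is called illustrative, the sample size is pragmatic, no retention threshold or progression rule is stated, and the plan will estimate the ICC and combine it with other evidence before sizing the later trial. That stands: neither enrolment nor any stated decision changes.

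A second objection is that the denominator is not settled. Section 11 recruits until 72 dyads are reached, while sections 13 and 25 treat 72 as those who complete, out of up to 100 enrolled. On 100 enrolled, the adjusted interval at ICC 0.01 (69.6% to 88.1%) is slightly narrower than the printed one, so there is no overstatement at that ICC. This also stands, and is why the denominator must be stated. It does not rescue the printed figure as a clustered calculation, because that figure is the unadjusted result for 72.

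The 72 might also be read as four times the 18 effective dyads left by the division of 20 by 1.09. That does not help: with 72 actual dyads in clusters of 18, the effective number is below 72 for any positive ICC.

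A reader might go further and infer that the borrowed ICC of 0.01 caused the overstated interval, or that the paragraph's 0.05 shows 0.01 to be wrong. The documents support neither. No ICC is reflected in the printed pooled interval. The 0.05 is offered "for a conservatively large true ICC=0.05", without a source or a named outcome, and only to illustrate estimation of the ICC. The 0.01 is itself above its source value of 0.006. Nor do the documents state the cluster unit or outcome behind 0.006; they only fail to connect it with retention by practice.

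**Conclusion.** The point holds in a limited form. The pooled retention interval does not contain the clustering the paragraph says it applies. On 72 dyads at 18 per practice it is too narrow by 1.7 points at the plan's own ICC (19.6 against 21.3) and by 7.4 points if the ICC were 0.05 (27.0). The single ICC offered for retention has no support in the documents specific to that outcome or to pediatric practices, so one interval understates the uncertainty. It would be wrong to say that all the stated retention precision is overstated: the per-practice interval is, if anything, too wide.

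The sizes assume 80% retention, equal practice sizes and exact intervals on the effective sample size. The overstatement at ICC 0.01 also assumes a denominator of 72. This is a correction to a stated figure for a primary outcome. It does not put the pilot's design in doubt.

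**What to change.** In section 13:

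1. Correct the design-effect line to the actual cluster size. With 18 dyads per practice and ICC 0.01 it is 1 + 17 × 0.01 = 1.17, giving 72 / 1.17 = 61.5 effective dyads in all, or 30.8 per condition.
2. Apply it to the pooled interval and remove it from the per-practice interval.
3. Report the pooled interval over a range of ICCs: about 67.9% to 89.1% at 0.01, and about 64.1% to 91.1% at 0.05 as a sensitivity bound, not as the base case.
4. State the denominator for retention and keep it consistent with sections 11 and 25. If it is 100 enrolled at 25 per practice, the corresponding intervals are about 69.6% to 88.1% and 65.5% to 90.4%.
5. Replace the teen-smoking value with a practice-level ICC of retention from the FITLINE study if one can be computed, since that study was done with these sites and already supplies the 97% retention figure. Otherwise say why 0.01 is reasonable for retention.
6. Add a sentence that with four practices these intervals are optimistic.

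The cost is a change of text and numbers in one section. Enrolment and procedures are unaffected. The drawback is that the stated precision looks less favourable.

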25. LOCAL NUMBER OF SUBJECTS

200 parents and children in grades 1-12 (aged 6-17 years) (i.e. 100 parent-child dyads total) with asthma will be recruited from the practices (25 parent-child dyads/practice) to achieve a retention of N=144 parents and children (i.e. 72 parent-child dyads) at the end of the study (from the 4 practices) at 12 month follow-up.

If two siblings are eligible for Asthma Link and this study, both children may participate in Asthma Link clinical program but only one child per family may be allowed to participate in the research study. We will grant the parent/guardian permission to choose which child they would like to participate in the research arm of the study.

Up to 16 Pediatric providers participating in Asthma Link™ will be recruited from the participating practices to participate in this study.

Up to 50 School nurses participating in Asthma Link™ will be recruited from the schools that the children participating in the study attend to participate in this study.

Up to 4 Asthma Champions participating in Asthma Link™ will be recruited from the participating practices to participate in this study.

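### The design effect and effective sample size in the retention example do not fit 18 dyads per practice, and the two retention intervals treat clustering inconsistently; the effect on stated precision is small

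*Combined protocol and SAP*

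**What the plan says.** Section 13, under Sample size calculation, plans "72 parent-child dyads (36 per condition, 18 per practice". It bases that number on practical and feasibility grounds and then offers retention as an illustration of precision.

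The illustration proceeds by "applying an intra-class (pediatric practice) correlation of 0.01". It prints "design effect= $1.19 = 1 + [1 + 0.01 \times 9" and, in the same sentence, divides 20 by 1.09 to reach an effective size of about 18 dyads per condition. For 80% retention it then gives 95% intervals of "51.9%, 95.7%) for each practice separately or (68.9%, 88.5%) combining all 4 practices". The interval method is not named.

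The next sentence, on the precision of the ICC, returns to the planned size: "A sample of 18 dyads per practice (36 per condition").

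The plan also distinguishes enrolment from completion. Section 13 says "we will potentially enroll up to 100 parent-child dyads" so that 72 complete, and Section 25 gives "25 parent-child dyads/practice) to achieve a retention of N=144 parents and children (i.e. 72 parent-child dyads" at 12 months. Section 11, by contrast, says recruitment runs until 72 dyads (18 per site) are recruited.

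**The concern.** Retention is one of the three primary trial outcomes in Section 4, and Section 13 says that the pilot's retention and ICC estimates will help to size the later cluster trial. A reader relies on this paragraph to see how well four practices can estimate retention.

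Three values of the design effect appear in one sentence, and none is the value for the planned practice size. The effective size starts from 20 per condition where the plan has 36. Neither interval uses that effective size: the single-practice interval looks as if it rests on fewer than 18 dyads, and the pooled interval looks as if it ignores clustering. At stake is whether the stated precision can be traced to the planned design.

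**Working it through.** **Inputs.** 18 dyads per practice, 36 per condition, 72 in all, 4 practices; ICC 0.01; retention 80% (all Section 13). Up to 100 enrolled, 25 per practice (Sections 13 and 25).

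**Design effect.** The formula is 1 + (m − 1) × ICC, with m dyads per practice.

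- As printed: 1 + [1 + 0.01 × 9] = 2.09.
- Value printed: 1.19, which is 1 + 19 × 0.01 and fits m = 20.
- Value used: 1.09, which is 1 + 9 × 0.01 and fits m = 10.
- Planned m = 18: 1 + 17 × 0.01 = **1.17**.

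**Effective size.**

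- Printed: 20/1.09 = 18.3 per condition. Twenty per condition over two practices is 10 per practice, consistent with the multiplier 9. The printed 1.19 would give 20/1.19 = 16.8.
- Planned: 36/1.17 = **30.8 per condition**, and 72/1.17 = **61.5 overall**.

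Section 24 still speaks of recruiting 40 children, which is 10 per practice. The calculation may be a carry-over from a design of that size, but the document does not say so.

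**Retention intervals.** These are exact (Clopper-Pearson) 95% intervals at 80%, with a non-integer count allowed where 0.8n is not whole.

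| Basis | n | Interval | Width (points) |
|---|---|---|---|
| Printed, one practice | – | 51.9% to 95.7% | 43.8 |
| 12/15 | 15 | 51.9% to 95.7% | 43.8 |
| One practice as planned | 18 | 54.8% to 94.8% | 40.0 |
| Printed, pooled | – | 68.9% to 88.5% | 19.6 |
| 72 dyads, no design effect | 72 | 68.9% to 88.5% | 19.6 |
| 72 dyads, design effect 1.17 | 61.5 | 67.9% to 89.1% | 21.2 |
| 100 enrolled, design effect 1.24 | 80.6 | 69.6% to 88.1% | 18.5 |

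*One practice.* The printed interval is reproduced by n = 15, not n = 18. The nearest whole counts at n = 18 give 52.4% to 93.6% (14/18) and 58.6% to 96.4% (15/18), so rounding the count does not explain it. Both 18/1.17 = 15.4 and 18/1.19 = 15.1 round down to 15, which suggests that a design effect was applied to a single practice. That origin is an inference. A between-practice design effect does not belong in an interval for one practice.

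*Pooled.* The printed interval is reproduced exactly by 72 dyads with no clustering adjustment. Adding the design effect moves the lower limit by about 1.0 point and the upper by 0.6.

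*Denominator.* If retention is measured on 100 enrolled, the design effect is 1 + 24 × 0.01 = 1.24 and the effective size is 100/1.24 = 80.6. The pooled interval is then slightly narrower than the printed one. For one practice, 20/25 gives 59.3% to 93.2%.

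*Sensitivity.* At ICC 0.05 and 72 dyads, the design effect is 1 + 17 × 0.05 = 1.85, the effective size is 72/1.85 = 38.9, and the pooled interval is 64.1% to 91.1%.

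**The case against.** The strongest defence is that this is an illustrative calculation in a pilot sized on pragmatic grounds. No test, threshold or sample size depends on it. The formula may be one correct value (1.09) surrounded by typographical errors, and its bracketing was read from a PDF. That is fair as to weight. It does not rescue the content: even with the bracket set aside, 1.19 and 1.09 disagree, and 20 per condition is not 36.

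Four stronger readings are tempting, and the documents do not support them.

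- *Neither interval matches the planned size.* The pooled interval does match 4 × 18 = 72; its fault is only the missing design effect.
- *The plan overstates its precision.* The direction is not settled. On 72 dyads the adjusted pooled interval is a little wider than printed; on 100 enrolled it is a little narrower. The per-practice interval is wider than it need be, and an effective size of 18 understates the 31 available, so both of those errors are conservative.
- *These intervals are the sole justification for 72 dyads.* Section 13 rests the number on practical grounds and also gives a precision statement for the ICC.
- *The wider interval at ICC 0.05 shows a larger error.* The plan chose 0.01 for retention, against 0.006 from prior studies, and uses 0.05 only to illustrate precision of the ICC itself. The wider interval is a sensitivity figure.

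**Conclusion.** The point holds and is minor. The design effect is inconsistent within one sentence, and the effective size belongs to 10 dyads per practice; for the planned design they are 1.17 and about 31 per condition (61.5 overall). The single-practice interval is about 4 points too wide for n = 18, and the pooled interval leaves out an adjustment worth about 1 point or less at each limit.

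These sizes assume ICC 0.01, 80% retention, equal practice sizes, exact intervals, and 72 as the retention denominator. With 100 enrolled as the denominator, the pooled discrepancy is of similar size in the other direction. No sample-size decision changes.

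**What to change.** Revise the one paragraph in Section 13:

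1. Give the design effect as 1 + 17 × 0.01 = 1.17 and the effective size as 36/1.17, about 31 per condition (61.5 overall).
2. State whether the retention denominator is 72 or the dyads enrolled (up to 100). If the latter, use 25 per practice, a design effect of 1.24 and a pooled interval of about 69.6% to 88.1%.
3. Give the single-practice interval at the actual n with no between-practice design effect (about 54.8% to 94.8% for 18), and the pooled interval with the design effect (67.9% to 89.1% on 72).
4. Name the interval method.
5. Optionally, add the pooled interval at ICC 0.05 (64.1% to 91.1% on 72), labelled as a sensitivity figure.

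The cost is a short rewording. No procedure, enrolment target or analysis changes.

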11. PROCEDURES INVOLVED*

Randomization. Two groups of two practices (4 practices in total) will be matched based on comparable size and percent of minority patients. Within each pair, practices will be randomly allocated to Asthma Link or the comparison condition, using a computerized function. This will result in two practices randomized to the Asthma Link condition and two practices randomized to the Enhanced Usual Care comparison condition.

Recruitment will be performed from each practice site until the target n=72 parent-child dyads (18 per site) are recruited. (see section 13 on “Sample size calculation”) Recruitment will begin during the 2021-2022 academic school year.

Procedure Steps:

1. Research coordinator (RC) identifies potentially eligible patients (children aged 6-17 years (enrolled in grade 1-12) years and prescribed a daily inhaled corticosteroid per medical record from most recent visit scheduled for a clinic visit) through the practice's office scheduling and medical record system (e.g., Epic). RC will also collect that patient's name, DOB, mailing and email addresses, phone number, insurance type (as a proxy for socioeconomic status), list of

INVESTIGATOR STUDY PLAN

medications, number of emergency room visits, number of hospital admissions and number of oral steroid courses for asthma relief.

2. RC creates a Lilac Form for any potentially eligible patients as described above. (Lilac form is an indicator to the medical provider seeing the patient that this patient is potentially eligible for study.)

3. Asthma Link condition: As part of clinical practice, medical provider will determine if patient is struggling with taking daily asthma medicine. If YES, then will introduce Asthma Link by saying “There is a clinical program that allows for your child to receive their daily asthma medicine at school supervised by the school nurse.” Child can be enrolled in Asthma Link per the usual clinical steps (see Asthma Link steps).

- After they are enrolled in Asthma Link, medical provider will give family one-page description of study (see Flyer) and state “Researchers at UMass are performing a study of children who are participating in Asthma Link, would you be interested in hearing more?”

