Statistical Analysis: To assess feasibility outcomes in Aim 1, we will estimate parameters relevant for planning a larger study, including standard deviations of outcomes and ICC. We will also conduct preliminary analyses of the impact of Asthma Link™ on asthma outcomes. We will compare participants in the two arms (Asthma Link™ and comparison group), using methods such as parametric or nonparametric t-test or Poisson regression, depending on the observed outcome distribution. Some outcomes may have a Poisson distribution, such as hospital admissions, while spirometry values may be continuous. Intent-to-treat and completer analyses will be performed. The data collected in this proposal will provide estimates of trial retention, ICC, standard deviation, and effect size. We will use these and data published in the literature to estimate sample size for a larger trial. The secondary outcomes analyses of asthma health outcomes will be exploratory by necessity given the pilot nature of this study.

INVESTIGATOR STUDY PLAN

Data will be collected at baseline (study entry), and at 3-, 6-, and 12-month follow-up in the privacy of the parent/child's home as the parent/child survey will be sent through email, in the pediatric practice staff's office or home (for pediatric provider and asthma champion surveys which will be sent through email), in the school nurse office or home (for school nurse surveys which will be sent through email). Assessments will be pre-tested to ensure the time burden does not exceed 30 minutes. The parent/student survey and assessment tools for this study will be adapted from [name] prior adolescent smoking cessation trials and our pre/post study^{14,18}. Data confidentiality will be emphasized on the surveys and verbally by Research Coordinator, and by the use of a unique study identification number.

Data Management: The surveys will be conducted either over the phone or by using the REDCap™ system, a nationally used secure, web-based database application (<http://project-redcap.org>) that provides: 1) an intuitive interface, 2) audit trails for tracking data manipulation and export, 3) procedures for importing data from external sources, 4) easy development of web survey tools and 5) automated export procedures to various statistical packages.

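### The 95% interval of (0.018, 0.094) given for the practice ICC cannot come from four practices of 18 dyads; standard methods give intervals about 2.5 to 8 times as wide

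*Combined protocol and SAP*

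**What the plan says.** Section 13 (Sample size calculation) sets the sample at "72 parent-child dyads (36 per condition, 18 per practice") and then states that this yields "95% confidence intervals for practice ICC of (0.018, 0.094) for a conservatively large true ICC=0.05". It cites a paper on sample size for ICC estimation but gives no formula and no number of clusters other than the trial's own.

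The number of practices is fixed elsewhere. Section 11 (Randomization) says "Two groups of two practices (4 practices in total) will be matched based on comparable size and percent of minority patients", and Section 22 says "This pilot feasibility study will take place in 4 Pediatric Primary Care practices in Worcester MA". Section 25 allows enrolment above the target: dyads "will be recruited from the practices (25 parent-child dyads/practice").

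Section 13 (Statistical Analysis) lists the ICC among the pilot's products: "we will estimate parameters relevant for planning a larger study, including standard deviations of outcomes and ICC". The pilot ICC will not be used alone. The sample size text combines it with "results of previous adequately powered interventions to calculate sample size requirements for our large cluster RCT", and the analysis text adds "We will use these and data published in the literature to estimate sample size for a larger trial".

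**The concern.** A practice-level ICC compares variation between practices with variation within them. Four practices give at most three degrees of freedom for the between-practice part, and adding dyads within a practice does not change that. An interval that excludes both zero and 0.10 is not credible from so few clusters.

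What is at stake is how far a planner can trust the pilot's ICC. As an illustration with clusters of 18, the design effect 1 + 17 × ICC is 1.3 at 0.018, 2.6 at 0.094 and 11.1 at 0.593. A reader who accepts the printed interval would think the pilot confines the design effect to about 1.3 to 2.6, which it cannot do.

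**Working it through.** **Inputs.** k = 4 practices (Sections 11 and 22); m = 18 dyads per practice (Section 13); ICC r = 0.05 and 95% confidence, taken as two-sided (Section 13). Assumptions: equal practice sizes, a normal outcome and a one-way random-effects model. The printed width is 0.094 − 0.018 = 0.076.

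**The plan's own figure.** It could not be reproduced at k = 4 by any method below. Reading the design as 2 × 18, 2 × 36, 4 × 25, 4 × 36, 4 × 72, 18 × 4, 36 × 4 or 72 × 4 (clusters × size) did not reproduce it either.

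**Formulas at an estimate of 0.05.**

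- F ratio: F = (1 + 17 × 0.05)/(1 − 0.05) = 1.85/0.95 = 1.947.
- Exact F, df 3 and 68: the critical values are 3.315 and 0.0715, so F/Fcrit is 0.587 and 27.23. Each limit is (F/Fcrit − 1)/(F/Fcrit + 17).
- Large-sample: SE = √{2(1 − r)²(1 + 17r)²/(18 × 17 × d)}. With d = k − 1 = 3 it is 0.082; with d = k = 4 it is 0.071. Limits are r ± 1.96 SE.
- Fisher z: z = ½ ln F, with variance (a) ½[1/(k − 1) + 1/(k(m − 1))] = 0.174 or (b) m/[2(m − 1)(k − 2)] = 0.265, then back-transformed.
- Logit: limits formed on the logit scale, so positive by construction.

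| Method | Limits | Width | Multiple of 0.076 | Multiple if cut at 0 |
|---|---|---|---|---|
| Large-sample, d = 4 | (−0.089, 0.189) | 0.278 | 3.7 | 2.5 |
| Large-sample, d = 3 | (−0.111, 0.211) | 0.322 | 4.2 | 2.8 |
| Fisher z (a) | (−0.036, 0.333) | 0.369 | 4.9 | 4.4 |
| Fisher z (b) | (−0.043, 0.431) | 0.474 | 6.2 | 5.7 |
| Logit | (0.002, 0.608) | 0.607 | 8.0 | 8.0 |
| Exact F, 3 df | (−0.023, 0.593) | 0.616 | 8.1 | 7.8 |

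**Allowing for arm and pair.** Removing the arm difference leaves 2 df, and exact F gives (−0.029, 0.808). Removing arm and pair leaves 1 df, and it gives (−0.036, 0.991).

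**More dyads per practice.** With 25 per practice, exact F gives (−0.012, 0.556), 7.5 times the printed width. The large-sample form with d = k gives (−0.068, 0.168), 3.1 times, or 2.2 times if cut at 0. With four practices and unlimited dyads, exact F still gives (0.017, 0.423), and the large-sample form with d = k − 1 gives (−0.026, 0.126).

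**How many practices of 18 would be needed.** Fisher z returns (0.018, 0.094) at 55 to 57 practices, depending on the variance form. The large-sample form matches on width only, at 54 to 55. Exact F matches closely on width at 59, giving (0.021, 0.097), and on the upper limit at 65, giving (0.022, 0.094).

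**Conditioning on a true ICC of 0.05.** The sentence speaks of a true ICC, so the sampling behaviour was checked as well (3 df, one million draws of F).

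- The middle 95% of ICC estimates is (−0.050, 0.233). About 33% of estimates are zero or negative, and 34% fall inside the printed limits.
- The median exact-F width, cut at 0, is 0.534, or 7.0 times the printed width. It is below 4 times in 19% of pilots and no wider than the printed interval in 3.5%.
- A binary check does not depend on normality: 400,000 beta-binomial data sets at the plan's 80% retention and ICC 0.05. The middle 95% of estimates is (−0.051, 0.237), with 35% inside the printed limits.

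**The case against.** The strongest reply is that little depends on the figure. The 72 dyads are justified by pragmatics, and no endpoint, randomisation step or analysis uses the interval. Section 13 warns about imprecision in small pilots on both sides of the sentence and commits to combining the pilot ICC with outside results. All of that is true, and it limits the consequence. It does not correct the number: a general caveat beside a specific, falsely tight interval leaves the reader with the interval.

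A second reply is that the method is not shown and the cited paper is not available here, so some unlisted method might apply. That rules out saying how the error arose. It does not make the figure plausible, since every standard method tried at four practices gives at least 2.5 times the width, and the sampling range at a true ICC of 0.05 is also far wider.

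Third, the multiple depends on choices. The 2.5 end uses the large-sample form with divisor k and limits cut at 0; with the usual divisor k − 1 it is 2.8. Only Fisher z matches both printed limits at a larger number of practices. A logit lower limit is slightly positive. These points affect how the range is labelled, not the conclusion.

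**Conclusion.** The concern holds. The printed interval claims a precision that four practices of 18 cannot give. At an estimate of 0.05 it is too narrow by about 2.5 to 8 times, with the exact-F and logit intervals at the upper end; removing arm or pair makes the gap larger. The interval calculations assume equal practice sizes and a normal one-way model, and the binary simulation supports the sampling-range result without normality. The consequence is confined to overstated precision for one planning parameter. It should be fixed because it is wrong as written and is the only precision figure offered for the ICC.

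**What to change.** Delete the sentence. This is the simpler course, because the protocol does not specify the model from which the ICC will be estimated.

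If an interval is kept, compute it for four practices and name the method, the degrees of freedom and the distributional assumption. One example is about 0 to 0.59 for an estimate of 0.05 (exact F, one-way random effects, normal outcome, 3 df, truncated at 0), with a note that it widens if arm or pair is removed.

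In either case, report the pilot ICC with the interval actually obtained when it is carried into the planning of the larger trial.

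The cost is protocol wording and a less favourable, or absent, precision statement. The target of 72 dyads, the randomisation and the endpoints do not change.
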